Document Title:

ArtiFascia® Clinical Investigation Plan-Pivotal Study

Document I.D.: CLN-01-1011
Date: 3.2.21

Rev.: 05

Page 1 of 6

CLINICAL INVESTIGATION PLAN

A PROSPECTIVE, RANDOMIZED, CONTROLLED MULTI-CENTER STUDY OF ARTIFASCIA® DURAL REPAIR PATCH COMPARED WITH COMMERCIALLY AVAILABLE DURAL SUBSTITUTES

NEOART STUDY

Protocol Number: CLN-01-1011

Revision 05

Date: February 03, 2021

NCT04145544

Title	A Prospective, randomized, controlled multi-center study of ArtiFascia® Dural repair patch compared with commercially available dural substitutes- NEOART Study .
Device	ArtiFascia®
Intended Use	ArtiFascia® is indicated as a dural substitute for the repair of dura matter.
Study Design	Prospective, randomized, multi-center, two-arm, single blind, parallel group clinical study.
Study Objective	To evaluate the safety and effectiveness of ArtiFascia® in comparison with commercially available dural substitutes in subjects requiring Dural repair following neurosurgery.
Study Population	Men and women scheduled for an elective cranial surgery that requires Dural repair, that meet the inclusion/exclusion criteria and can provide written Informed Consent.
Enrollment	A total of 90 subjects (81 + 9 to account for 10% loss to follow-up rate) will be enrolled and implanted with test or control device. To account for an assumed 10% loss to follow-up rate, additional 9 subjects will be enrolled (60 in the ArtiFascia® group and 30 in the control group).
Study Groups	Subject will randomly be allocated into one of the following two groups in a 2:1 allocation ratio of ArtiFascia and control groups: 
• Experimental group: ArtiFascia® device• Control group: Other commercially available suturable dural substitutes (e.g. Duraform, Duragen, Durepair)
Randomization	Study population will be randomized using 2:1 ratio of experimental group (ArtiFascia device recipients) to control group (commercially available dural replacement recipients) respectively and preoperatively blinded.
Duration of Study	Completion of active enrolment is anticipated to last approximately 2 years. The primary endpoint will be achieved when the final study subject has completed a 6-months follow-up. The entire duration of the study is anticipated to require a total of 2.5 years.

Study Enrollment Start Date: November 2019

Estimated Study Enrollment End Date: November 2021

Estimated Study Follow Up Completion: May 2022

Investigational sites	Up to 10 centers in Europe and Israel are planned to participate in this study.
Duration of Subject Participation	Each subject will be followed from pre-treatment to 6 months. After discharge, subjects will come for a clinic visit at 4-6 weeks and at 6 months post implantation.
Primary Endpoint	Absence of CSF fistula (drainage from wound or sinus) and pseudo-meningocele within 6 months post-operative as evaluated by MRI imaging.
Secondary Endpoints	
1. Wound healing assessment2. Device Handling Characteristics (i.e., Ease of Use, strength Suturability, Seal Quality)3. Magnetic Resonance Imaging at the 6-month follow-up, to determine the presence or absence of the following measures:
• Adhesion formation• New tissue formation• Brain edema adjacent to device implant site
Inclusion Criteria	
1. Subject between the ages of 18-752. Subject is scheduled for an elective cranial surgery with a dural damage that can be completely repaired/closed by a suturable dural substitute (ArtiFascia device or other commercially available dural substitutes)3. Subject has undergone imaging (such as, MRI) in the past 6 months before enrolment4. Surgical wound is expected to be Class I/clean5. Subject understands the study requirements and the treatment procedures and provides written Informed Consent before any study-specific tests or procedures

are performed

6. Subject is able and willing to adhere to the required follow-up visits and testing
- Exclusion Criteria**
 1. Pregnant women or interest in becoming pregnant during the duration of the study
 2. Subject has known hydrocephalus
 3. Subject is unable to undergo MRI after the surgery
 4. Subject's life expectancy is less than 12 months
 5. Subject has a local or systemic infection (e.g. urinary tract infection (UTI), active pneumonia) or evidence of any surgical site infection, fever $> 38.3^{\circ}\text{C}$, positive blood culture and/or a positive chest x-ray for acute infectious process
 6. Subject will require use of dural adhesive or sealant
 7. Subject is intended to undergo craniectomy wherein bone flap will not be returned
 8. Subject with suspected low success in wound healing due to past treatments (e.g. chemotherapy, radiation therapy, severe diabetes etc.) or other conditions (e.g. severe peripheral vascular disease, long standing steroids treatment)
 9. Subject has been clinically diagnosed with malignancy (other than basal cell carcinoma or low-grade glioma), uncontrolled diabetes ($\text{A1C}>6.5\%$), sepsis, systemic collagen disease.
 10. Subject had chemotherapy and/or radiotherapy in the past 12 weeks before surgery or is planned to have chemotherapy or radiotherapy less than 12 weeks after surgery.
 11. Subject is an acute cranial trauma surgical case
 12. Subjects with a concurrent disease that would place the patient in excessive risk to the planned surgery
 13. Subject had a previous neurosurgery in the same

anatomical site

14. Subject with other undesirable symptoms defined by the principal investigator
15. Patient has clinically significant coagulopathy as determined by the surgeon
16. Subject is participating in another clinical trial using similar investigational devices/drugs

Visits and Procedures

Baseline: The baseline visit will include an assessment of subject qualifications for inclusion in the study according to the inclusion/exclusion criteria. Informed consent must be signed. Medical data will be taken including subject's medical complaints, medical history, neurological assessment, and medications use. Blood tests will include CBC and chemistry (according to site standards).

Randomization and Procedure: Vital signs (blood pressure, temperature, pulse rate), as well as height and weight will be measured prior procedure.

The subject will be randomized during the index procedure after the physician confirmation that the subject fulfills all inclusion criteria. If found eligible, subject will be enrolled and randomized to one of the 2 groups: experimental group (ArtiFascia device recipients) or control group (commercially available suturable dural substitutes recipients). In addition, recruitment of subjects planned to undergo surgery in posterior fossa area will be limited to 15% of the total study sample size to ensure comparability to common rates of this procedure reported in the literature.

Procedure will be performed under general anesthesia. ArtiFascia® or the control device will be implanted and sutured according to device IFU. Immediately post procedure essential data will be recorded including procedural details, surgeon's opinion on device ease of use and suture-ability, and other procedure related complications and medications prescribed.

Post operation the subject will stay at the hospital according

to site standards and physician discretion.

Follow-up: After discharge, all subjects will have regular follow-up visits at 4-6 weeks and at 6 months post procedure.

At discharge and at 4-6 weeks and 6-month visits, the following examinations may be performed:

Physical examination of the surgical site to test CSF leakage
Vital signs (blood pressure, temperature, pulse rate)– only at discharge and at 4-6 weeks

Standard assessment of general neurological health

Physical examination of the surgical site to test wound healing

Adverse events will be assessed on a continuous basis from the baseline through the study completion at 6 months, and all events whether related or not related will be reported.

Magnetic Resonance Imaging will be performed 6 months post operation in all subjects.

During the follow-up period MRI may be performed if deemed necessary. In case MRI is performed, the presence of pseudo-meningocele or other internal CSF leakage in the implant area, will be evaluated. If MRI is performed more than 3 months post operation and does not indicate presence of a leak, this data will be used to determine the leak rate and the subject will not be required to undergo an additional MRI at 6 months.

STATISTICAL ANALYSIS PLAN (SAP)

Study No.: **CLN-01-1011 (NEOART)**

Study Title: **A Prospective, randomized, controlled multi-center study of ArtiFascia® Dural repair patch compared with commercially available dural substitutes.**

Device: **ArtiFascia®**

Intended Use: **ArtiFascia® is indicated as a dural substitute for the repair of dura matter.**

Date: **14AUG2022**

Version: **Version 2.0**

NCT: **04145544**

Sponsor: **Nurami Medical Ltd.
[name]**

Statistical Considerations

Randomization

Eligible Subject will be randomly allocated into one of the two treatment groups by Interactive Response Technology (IRT) in a 2:1 allocation ratio of ArtiFascia and control group respectively, using blocks stratified by study sites and surgery in posterior fossa area or not.

The primary endpoint will be absence of CSF fistula (drainage from wound or sinus) and pseudo-meningocele within 6 months post-operative evaluated by Magnetic Resonance Imaging evaluation and physical examination of the surgical site.

Sample Size Rationale

The sample size for this study is calculated assuming the following assumptions: power of 80%, 5% one-sided significance level, 2:1 allocation ratio of ArtiFascia and control groups respectively, the absence of CSF leak rate in both the ArtiFascia and control groups is 97%, non-inferiority margin of -10% and the Chi-square test statistics.

Assuming the above assumptions a sample size of 81 subjects will be required in total. Allowing for a potential 10% dropout, 90 subjects should be randomized (60 in the ArtiFascia® group and 30 in the control group).

Blinded Sample Size Reassessment

To examine whether the assumed absence of CSF leak rate of 97% in the sample size calculation, a non-comparative assessment of the pooled absence of CSF leak rate will be performed after 50% of the randomized subjects will complete the study.

In case that the pooled absence of CSF leak rate will be less than the assumed 97%, the sample size will be upsized accordingly.

Primary Efficacy Endpoint Analysis

The primary endpoint: CSF leakage absence at month 6 will be tested for non-inferiority of the CSF leakage absence rate in the ArtiFascia group, to that in the control group, using a non-inferiority margin of -10%.

The estimated rates of CSF leakage absence at month 6 for each treatment group and the difference between the treatment groups (ArtiFascia - Control) will be calculated.

Exact one-sided 95% confidence interval will be calculated for the difference between the treatment groups in CSF leakage absence rates at month 6 using the Farrington-Manning method.

Non-inferiority will be concluded if the lower limit of the one-sided 95% exact confidence interval of the difference between the two study arms of CSF leakage absence rate at month 6 will be above the non-inferiority margin of -10%.

Secondary Efficacy Endpoints

The following secondary efficacy endpoints will be compared between the study treatment groups using Fisher exact test (for endpoints with more than 2 categories, collapsing of categories with low frequency will be considered):

1. Wound healing assessment (Clean and/or fully healed vs. Infected),) which will be considered as key secondary efficacy end point
2. Device Handling Characteristics (Ease of Use, Strength, Suturability, Seal Quality)
3. Magnetic Resonance Imaging at the 6-month follow-up, to determine the presence or absence of the following measures:
 - Adhesion formation
 - New tissue formation
 - Brain edema adjacent to device implant site

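### The primary endpoint is defined within 6 months but tested at month 6, and no rule scores a leak that was treated and resolved earlier, so such a leak can count as success.

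*SAP*

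**What the plan says.** **Definition.** At the end of its Randomization section, the SAP defines the primary endpoint as absence of CSF fistula (wound or sinus drainage) and pseudo-meningocele, "within 6 months post-operative evaluated by Magnetic Resonance Imaging evaluation and physical examination of the surgical site". The protocol's Primary Endpoint row names one source only: "pseudo-meningocele within 6 months post-operative as evaluated by MRI imaging".

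**Analysis.** Under Primary Efficacy Endpoint Analysis the SAP states: "CSF leakage absence at month 6 will be tested for non-inferiority". The estimated rates, the confidence interval and the non-inferiority criterion all refer to month 6 as well.

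**Data collection (Protocol, Follow-up).**

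- Visits: "At discharge and at 4-6 weeks and 6-month visits, the following examinations may be performed". The list includes examination of the surgical site for CSF leakage.
- MRI: done in all subjects at 6 months. In addition, "During the follow-up period MRI may be performed if deemed necessary", and "In case MRI is performed, the presence of pseudo-meningocele or other internal CSF leakage in the implant area, will be evaluated".
- Interim MRI: a scan after 3 months that shows no leak is used for the leak rate and replaces the 6-month scan. Nothing is said about an interim scan that does show a leak.
- Adverse events: "Adverse events will be assessed on a continuous basis from the baseline through the study completion at 6 months". Neither document links them to the primary endpoint.

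**The concern.** The definition is cumulative, while the analysis reads as the state at one time. A fistula that drains in week 10, is repaired and is dry at the last visit is a failure under the first and a success under the second. No scoring rule settles which applies, and neither document says whether unscheduled examinations or adverse-event reports feed the endpoint.

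Treated leaks are the ones most likely to have resolved by the final assessment, so the leaks at risk of being dropped include the clinically important ones. In a non-inferiority comparison, missing the same share of events in both arms shrinks the observed difference and makes the claim easier to reach. Events are also few: at the assumed 97% leak-free rate, 90 × 0.03 = 2.7 leaks are expected in the whole trial, so the scoring of a single subject can decide the result.

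**Working it through.** **1. The plan's sample size.** Inputs (SAP, Sample Size Rationale): leak-free rate 97% in both arms, margin 10 points, one-sided 5%, power 80%, ratio 2:1.

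n(control) = (1.645 + 0.842)² × 0.97 × 0.03 × (1 + 1/2) / 0.10² = 26.99, so 27. ArtiFascia 2 × 27 = 54; total 81; 81 / 0.9 = 90. Both stated figures reproduce. The point concerns scoring, not the sample-size arithmetic.

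**2. Following one subject through the text.** Take external wound drainage that starts after the 4–6 week visit, is treated without MRI, and has stopped by month 6.

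| Text | Score |
|---|---|
| SAP definition, within 6 months | Failure, if the leak reaches a named source |
| SAP analysis and decision rule, at month 6 | Success |
| 6-month examination and MRI | No leak seen |
| Adverse-event record | Leak recorded, no link to the endpoint |

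Between week 6 and month 6 (about week 26) there are some 20 weeks with no scheduled examination.

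**3. Effect on the false-claim probability.** The documents give no rate of missed leaks, so the share f is an assumption. True leak rates are set on the margin: 3% in control (100% − 97%) and 3% + 10% = 13% for ArtiFascia. If a share f goes uncounted in both arms, the recorded rates are 13%(1 − f) and 3%(1 − f), and the recorded difference is 10(1 − f) points. The test is the exact one-sided 5% test with Farrington-Manning ordering, maximised over the nuisance rate.

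| f | Recorded rates | Difference (points) | False claim, 60/30 | False claim, 54/27 |
|---|---|---|---|---|
| 0 | 13.00% vs 3.00% | 10.0 | 4.5% | 3.5% |
| 5% | 12.35% vs 2.85% | 9.5 | 5.4% | 4.1% |
| 10% | 11.70% vs 2.70% | 9.0 | 6.5% | 4.8% |
| 20% | 10.40% vs 2.40% | 8.0 | 9.2% | 6.7% |
| 25% | 9.75% vs 2.25% | 7.5 | 10.9% | 8.0% |
| 33% | 8.71% vs 2.01% | 6.7 | 14.2% | 10.7% |

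60/30 assumes no dropout; 54/27 is the evaluable number the plan is sized for.

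**4. Effect of one subject.** At 60/30 with no control leaks, one ArtiFascia leak gives a lower limit of −7.8% (exact p = 0.019, pass). Two give −10.1% (p = 0.053, fail). The asymptotic score test would pass two (z = 1.72 against 1.645) and fail three (z = 1.29), but the SAP specifies an exact interval. At 54/27 both methods pass one leak and fail two.

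**5. Effect on the blinded reassessment.** The SAP enlarges the trial if the pooled leak-free rate at the halfway point is below 97%. If that means 45 subjects (half of 90), one leak gives 44/45 = 97.8% and no increase; two give 43/45 = 95.6% and an increase. One uncounted leak can therefore also prevent the increase.

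**The case against.** A reader might infer that a leak between visits is captured only as an adverse event and is lost to the endpoint even under the cumulative definition. The documents do not support that, for three reasons:

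- Unscheduled MRI is allowed and must then be read for pseudo-meningocele or other internal leakage. MRI is a named source, so a pseudo-meningocele imaged between visits can reach the endpoint.
- The SAP does not restrict surgical-site examination to scheduled visits. A fistula that was diagnosed and repaired would ordinarily have been looked at.
- Absence within 6 months, read literally, already makes any such leak a failure.

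A reader might also infer that sinus drainage has no route into the endpoint because only the surgical site is examined. That is weak: the term is undefined, and a sinus tract at the wound would be covered by that examination.

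On size, the shares are assumed, and with the routes above a small one is plausible. At 5–10% uncounted the false-claim probability is 5.4–6.5% at 60/30, and at 54/27 it stays below 5%. The one-leak reversal reflects the small trial and would follow from any misclassification. The public protocol is also a synopsis, so a fuller plan may contain the missing rule.

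All of this stands, and it limits the point to what the text leaves open. It does not remove the conflict between definition and analysis, or supply a rule for a leak that was found, treated and resolved.

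**Conclusion.** The point holds as a gap in scoring and a conflict of wording. The SAP defines a cumulative endpoint, tests and decides on a month-6 state, and says nothing about a leak that resolved in between. An analyst who follows the analysis section as written can score a repaired leak as success.

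Over assumed shares of 5–33% uncounted in both arms, the false-claim probability on the margin rises from 4.5% to 5.4–14.2% at 60/30, and from 3.5% to 4.1–10.7% at 54/27. This rests on true leak rates of 13% and 3%, equal under-counting in the two arms, and the exact test. Unequal under-counting could push the result either way. Confidence is medium, because only the synopsis is public. The change should be made, since it is cheap and single leaks can decide the result.

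**What to change.** 1. In the SAP's Primary Efficacy Endpoint Analysis, including the decision rule, replace *at month 6* with *within 6 months*, and align the sources named in the protocol's endpoint with the SAP's.

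2. Add to the endpoint definition:

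> A subject is a failure if a CSF fistula (drainage from wound or sinus), CSF leak or pseudo-meningocele is recorded at any time from implantation to the 6-month assessment, by scheduled or unscheduled examination, any MRI, or an adverse-event report, or if an intervention for one is recorded; later resolution does not change the score.

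3. Identify the adverse-event cases with a fixed term list before treatment arms are attached to the data, and use the same scoring in the blinded reassessment.

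**Cost.** SAP wording and a merge with adverse-event data already collected. Leak-free rates may come out slightly lower in both arms. If they fell to 96% or 95%, the plan's own formula would need 108 or 135 evaluable subjects instead of 81, and power at 54/27 would drop from 80% to about 70% or 62%; these rates are illustrative. The blinded reassessment already provides for an increase in that case. The study is single blind, so those who report adverse events may know the arm. The term list does not remove that reporting bias.

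### The 80% power claimed for 81 evaluable subjects comes from a normal-approximation formula; under the exact Farrington-Manning rule that decides the trial it is about 69%

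*SAP*

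**What the plan says.** The SAP, Sample Size Rationale, sets out the planning assumptions: "power of 80%, 5% one-sided significance level, 2:1 allocation ratio of ArtiFascia and control groups respectively", a 97% leak-free rate in both arms, and a "non-inferiority margin of -10% and the Chi-square test statistics". It concludes: "Assuming the above assumptions a sample size of 81 subjects will be required in total". Allowing for 10% dropout, this becomes 90 (60 ArtiFascia, 30 control). The Enrollment row of the protocol synopsis repeats 81 + 9 and gives no other basis.

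The SAP, Primary Efficacy Endpoint Analysis, decides the trial by another procedure. An exact one-sided 95% interval is calculated for the difference in "CSF leakage absence rates at month 6 using the Farrington-Manning method", and "Non-inferiority will be concluded if the lower limit of the one-sided 95% exact confidence interval" is above -10%.

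The SAP, Blinded Sample Size Reassessment, looks at the pooled rate once half the randomised subjects have completed: "In case that the pooled absence of CSF leak rate will be less than the assumed 97%, the sample size will be upsized accordingly".

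Neither document gives the power of the exact Farrington-Manning rule.

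**The concern.** The sample size is justified with one test and the trial is decided with another. With about 3% leaks per arm and a 10-point margin, the two can differ a good deal.

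The planning formula takes the variance of the difference at 97%/97%. The Farrington-Manning statistic takes it under the null hypothesis, where the rates must differ by 10 points, and that variance is larger. Expected leaks are also very few: 54 × 0.03 = 1.62 on ArtiFascia and 27 × 0.03 = 0.81 on control. A normal approximation is unreliable at such counts, and an exact procedure loses further power to discreteness.

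If the 80% does not hold under the actual rule, the sponsor carries a higher risk than stated of failing with a device that is truly as good as control. The reassessment would add false comfort, since a pooled rate at the assumed 97% would be taken to mean that power is on target.

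**Working it through.** **Inputs** (SAP, Sample Size Rationale and Primary Efficacy Endpoint Analysis): one-sided alpha 0.05; target power 0.80; 2:1 allocation; true rate 0.97 in both arms; margin 0.10; 10% dropout; decision by the exact one-sided 95% Farrington-Manning limit.

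**1. The plan's own figure.** For the control arm,

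n = (1.645 + 0.842)² × 0.97 × 0.03 × (1 + 1/2) / 0.10² = 26.99, rounded up to 27.

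This gives 27 control + 54 ArtiFascia = 81, and 81 / 0.9 = 90. Both figures reproduce. Pooled and unpooled variances coincide because the two rates are equal.

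**2. Effect of the restricted variance alone.** With 97% in both arms and 2:1 allocation, the maximum-likelihood rates constrained to a difference of -0.10 are 88.86% (ArtiFascia) and 98.86% (control). At 54/27:

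- Standard error under the margin: √(0.8886 × 0.1114/54 + 0.9886 × 0.0114/27) = 0.0475.
- Standard error at 97%/97%: √(0.97 × 0.03 × (1/54 + 1/27)) = 0.0402.
- Power = Φ[(0.10 − 1.645 × 0.0475)/0.0402] = Φ(0.546) = 70.7%.

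The same large-sample formula gives 75.2% at 90 and first reaches 80% at 102. The variance term therefore explains most of the loss.

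**3. Exact power.** All tables at each size were enumerated and ordered by the Farrington-Manning statistic at -0.10. The p-value was maximised over the nuisance rate, and non-inferiority was declared when p ≤ 0.05. Checking the boundary tables at differences down to -0.30, as inverting the test into an interval requires, changed no decision. At 54/27 the rule passes as follows:

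| Control leaks (of 27) | Probability at 97% | Most ArtiFascia leaks allowed (of 54) | Probability of meeting that limit | Product |
|---|---|---|---|---|
| 0 | 0.439 | 1 | 0.515 | 0.226 |
| 1 | 0.367 | 2 | 0.780 | 0.286 |
| 2 | 0.148 | 3 | 0.921 | 0.136 |
| 3 | 0.038 | 5 | 0.995 | 0.038 |

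These rows sum to 0.686. Four or more control leaks add 0.008, giving 0.694.

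**4. Across sizes, 97% in both arms:**

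| Evaluable (ArtiFascia/control) | Exact power |
|---|---|
| 81 (54/27) | 69.4% (maximum size 4.68%) |
| 84 (56/28) | 68.4% |
| 87 (58/29) | 68.5% |
| 90 (60/30) | 73.8% (maximum size 4.73%) |
| 93 (62/31) | 83.9% |

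Exact power stays above 80% at every larger 2:1 size checked, up to 165.

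**5. Sensitivity at 54/27 to the common true rate:** 55.3% at 95%, 61.4% at 96%, 69.4% at 97%, 79.8% at 98%.

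**6. Other readings at 54/27:** the asymptotic Farrington-Manning test, enumerated, has 70.3% power with type I error up to 5.8%. A plain Wald interval has 86.2%, but with type I error up to 23%. So even the interval closest to the planning formula does not behave as that formula assumes.

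**The case against.** The strongest reply is that 81 is correct for the method the SAP names. The planning test is disclosed, and planning on an approximation while analysing exactly is common practice. That stands as far as it goes: the number is no slip within its own formula. What fails is attaching 80% power to the decision rule actually used, because here the gap is about 11 points.

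Second, Farrington-Manning is often used as an asymptotic method, so the result could turn on how the word exact is read. On the asymptotic reading, enumerated power is 85.5% at 58/29 and 84.7% at 60/30. But the SAP calls the interval exact both where it is calculated and where it is used to decide. The asymptotic test also exceeds the stated 5% (about 5.8% to 6.2%), and at the planned 81 it still gives only 70.3%.

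Third, 69% is the figure after the full 10% loss. This is fair: with no loss power is 73.8%. No 2:1 size from 81 to 90 reaches 80% at the assumed rate.

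Fourth, type I error is controlled, so the shortfall cannot produce a false claim of non-inferiority. The SAP (14 August 2022) also postdates the protocol's estimated end of follow-up (May 2022). Both points lower the urgency. Actual accrual is not given, though, and the power statement can be corrected in either case.

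Finally, the reassessment names no recalculation formula, so it cannot be shown to repeat the planning approximation. What the text does support is that a pooled rate of 97% or more triggers no increase.

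**Conclusion.** The concern holds. The 80% power in the Sample Size Rationale is not a property of the trial's own decision rule. With a true rate of 97% in both arms, exact power is 69.4% at 81 evaluable, 73.8% at 90, and between 68% and 74% at the 2:1 sizes in that range. The chance of failing with identical devices is about 31% at 81 and 26% at 90, against the 20% implied. Under the exact rule, 80% is first reached at 93 evaluable, 12 more than planned. At the planned 54/27, a true rate of about 98% would be needed (79.8%), so 97% is the wrong benchmark for the reassessment.

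This rests on reading the interval as the exact unconditional one obtained by inverting the Farrington-Manning score test, and on evaluable subjects keeping the 2:1 ratio. The finding at 81 does not depend on the first assumption. The consequence is a higher risk of a false negative, with no inflation of type I error.

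**What to change.** In the SAP:

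- **Sample Size Rationale.** Replace the chi-square reference with the exact Farrington-Manning rule, say that exact means unconditional inversion of the score test, and restate power as about 69% at 81 evaluable and about 74% at 90 with no loss. Report power at 95%, 96% and 98% as well.
- **Blinded Sample Size Reassessment.** Specify that both the trigger and any new size are computed by enumerating the exact power of the same rule. Exact power rises and falls irregularly with sample size, so a closed formula will not do.

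The cost is SAP wording and one exact calculation. The stated power becomes less favourable, and no extra subjects are needed to correct it.

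If recruitment were still open and the sponsor wished to keep 80%, the requirement would be 93 evaluable. That means 93/0.9 = 103.3, so 104 randomised, or 105 to hold 2:1 exactly. This is a separate decision from correcting the statement.

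### The primary endpoint is defined as no leak within 6 months, but the SAP tests absence at month 6, so read literally an early leak that clears counts as a success

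*SAP*

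**What the plan says.** **Definition.** The Protocol synopsis (Primary Endpoint) gives "Absence of CSF fistula (drainage from wound or sinus) and pseudo-meningocele within 6 months post-operative as evaluated by MRI imaging". The SAP's endpoint paragraph, under Randomization, keeps the same period and adds a method of assessment: "within 6 months post-operative evaluated by Magnetic Resonance Imaging evaluation and physical examination of the surgical site". Both describe an event-free interval.

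**Analysis.** All four operative sentences of the SAP's Primary Efficacy Endpoint Analysis refer to a time point:

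- the test: "The primary endpoint: CSF leakage absence at month 6 will be tested for non-inferiority";
- the estimates: "The estimated rates of CSF leakage absence at month 6 for each treatment group";
- the confidence interval, for the "difference between the treatment groups in CSF leakage absence rates at month 6 using the Farrington-Manning method";
- the decision rule, which needs the lower limit of the "difference between the two study arms of CSF leakage absence rate at month 6 will be above the non-inferiority margin of -10" percent.

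**Follow-up.** The Protocol synopsis (Follow-up) lists this among the examinations at discharge, 4-6 weeks and 6 months: "Physical examination of the surgical site to test CSF leakage". MRI is scheduled for everyone at 6 months and may be done earlier if needed: "In case MRI is performed, the presence of pseudo-meningocele or other internal CSF leakage in the implant area, will be evaluated". A leak-free scan taken more than 3 months after surgery replaces the 6-month scan. There is no matching rule for an interim scan that shows a leak.

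**The concern.** A subject who leaks early and has healed by month 6 is a failure under the definition and a success under the literal analysis wording. The follow-up schedule allows such subjects to be found, because leakage is looked for well before month 6. A subject whose interim MRI shows a leak does not qualify for the waiver and is still due a month-6 scan. Nothing says whether a clear later scan overrides the leak on the interim scan.

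Whoever derives the analysis variable will work from the analysis section, which consistently points to month-6 status. The non-inferiority conclusion would then rest on a different variable from the stated primary endpoint. If the ambiguity is left open, the scoring rule could be settled after results are known, when a single subject may decide the outcome.

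**Working it through.** **1. Inputs (SAP, Sample Size Rationale and Primary Efficacy Endpoint Analysis).** Absence rate 97% in both arms, margin -10%, one-sided 5%, power 80%, 2:1 allocation, 81 evaluable, 90 randomized (60 and 30). The 2:1 ratio splits 81 into 54 ArtiFascia and 27 control.

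**2. Reproducing the plan's sample size.** Normal approximation, unpooled variance:

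n(control) = (z₀.₉₅ + z₀.₈₀)² × p(1-p) × (1 + 1/2) / 0.10² = (1.645 + 0.842)² × 0.97 × 0.03 × 1.5 / 0.01 = 26.99, rounded up to 27.

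Total 27 + 54 = 81, and 81/0.9 = 90. Both match the SAP.

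**3. Expected events.** 81 × 0.03 = 2.43 leaks in the whole trial.

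**4. Scoring of three types of subject.**

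| Subject | Definition (within 6 months) | Analysis text read literally (at month 6) |
|---|---|---|
| Leak on examination at discharge or 4-6 weeks, clear at month 6 | Failure* | Success |
| Pseudo-meningocele on interim MRI, clear month-6 MRI | Failure | Success |
| Leak present at month 6 | Failure | Failure |

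*Under the SAP's definition, which includes physical examination. The Protocol's definition names MRI only.

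**5. Effect of one rescored subject on the decision.** The statistic is the Farrington-Manning score

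z = (d + 0.10) / √[p̃₁(1-p̃₁)/n₁ + p̃₂(1-p̃₂)/n₂],

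where d is the observed difference in absence rates (ArtiFascia minus control) and p̃₁, p̃₂ are the maximum-likelihood rates constrained to differ by -0.10. The exact p-value is the largest tail probability over all control rates under that null.

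Example, 3 versus 1 leaks at 54/27: d = 51/54 - 26/27 = -0.0185, p̃₁ = 0.8829, p̃₂ = 0.9829, standard error 0.0504, so z = 0.0815/0.0504 = 1.618.

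| Leaks, ArtiFascia vs control (54/27) | z (critical 1.7335) | Exact p | Exact lower limit | Non-inferior? |
|---|---|---|---|---|
| 3 vs 1 | 1.618 | 0.064 | -10.7% | No |
| 2 vs 1 | 2.033 | 0.027 | -8.4% | Yes |
| 2 vs 0 | 1.542 | 0.083 | -11.2% | No |
| 1 vs 0 | 1.996 | 0.029 | -8.6% | Yes |

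Forgiving one ArtiFascia leak turns 3 vs 1 into 2 vs 1, a failure into a pass. Forgiving one control leak turns 2 vs 1 into 2 vs 0, a pass into a failure. So the effect can go either way.

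With 60/30 (no dropout, critical z 1.7282): 4 vs 1 fails (1.396) and 3 vs 1 passes (1.785); 2 vs 0 fails (1.721) and 1 vs 0 passes (2.152).

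At 54/27, asymptotic score limits give the same four decisions: -10.2%, -7.6%, -10.6% and -7.9%, in the order of the table.

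**6. How close trials of this size sit to the boundary.** The largest ArtiFascia leak count that passes with 0, 1, 2 or 3 control leaks is 1, 2, 3, 5 at 54/27 and 1, 3, 4, 5 at 60/30. Taking leaks as binomial with rate 0.03 in each arm:

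| | 54/27 | 60/30 |
|---|---|---|
| Fails, but passes with one ArtiFascia leak fewer | 17.6% | 14.0% |
| Passes, but fails with one control leak fewer | 12.1% | 17.5% |
| Sum | 29.7% | 31.5% |

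These shares measure sensitivity to one subject's classification, which any trial with few events has. They are neither error rates nor the chance that this wording reverses the result.

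**The case against.** The strongest reply is that the month-6 wording is shorthand. The SAP defines the endpoint once, over the full period, and the analysis section refers back to it by name. It already abbreviates fistula and pseudo-meningocele to leakage, so it may be abbreviating the window too, and no text says an early leak is forgiven. This is plausible, and the twice-stated definition favours it. But it is nowhere written, and if it is what was meant, the correction simply records it.

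Second, the Protocol's definition is evaluated by MRI, and the only MRI scheduled for all subjects is at 6 months, so that definition is closer to month-6 status than it first appears. This stands in part. The SAP's own definition, however, adds physical examination, and interim scans are evaluated for leakage, so the two readings can still diverge.

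Third, the shares in step 6 are not conditioned on a leak being early, detected and resolved. That is correct. The example counts carry the argument, and the shares are only context.

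Fourth, the correction may not be free. The Protocol says the visit examinations may be performed, which is weaker than a requirement, and a lower success rate could lead to a larger sample. Both points stand and are reflected in the cost below.

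**Conclusion.** The concern holds. The definition and the decision rule, as written, describe different variables, and no text reconciles them. The inconsistency is certain; that an early leak would actually be scored as a success depends on the literal reading, which is probably not the intended one.

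The consequence is that one subject's scoring can reverse the conclusion in either direction, as 3 vs 1 against 2 vs 1, and 2 vs 1 against 2 vs 0, show at 54/27. This rests on the SAP's margin and one-sided 5% level, on an exact unconditional Farrington-Manning test, and on 81 evaluable subjects split 2:1; similar reversals occur at 60/30. No effect on error rate or power is claimed, because the documents do not say how often leaks resolve. It should be fixed before unblinded analysis.

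**What to change.** Replace the month-6 wording in all four sentences of the SAP's Primary Efficacy Endpoint Analysis with the defined endpoint. Suggested content: a subject is a failure if a CSF fistula or pseudo-meningocele is found by physical examination of the surgical site, or on any scheduled or unscheduled MRI, from surgery through the month-6 assessment, whether or not it later resolves. State that a later clear scan does not override an earlier leak, and align the Protocol's definition, which names MRI only, with the SAP's.

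Use the same variable in the blinded sample size reassessment and say that the 97% refers to it. The SAP is dated 14 August 2022 and the Protocol estimated follow-up completion in May 2022. If the reassessment has already been done, report which variable it used.

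**Cost.** Wording only, with no visit or examination beyond those the Protocol already lists. The SAP should say how missing early examinations are handled, since the Protocol does not clearly require them. The observed success rate may be somewhat lower than under month-6 status, and the reassessment rule would then increase the sample size. If the 97% was in fact a month-6 rate and the cumulative rate were 96% or 95% in both arms (assumed values), the formula in step 2 gives 108 or 135 evaluable subjects, and dividing by 0.9 gives 120 or 150 randomized. If the 97% is already cumulative, 81 and 90 stand.
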